8.3.2 Laboratory Tests including Pregnancy Test

Absolute values and changes from baseline will be summarized for the following laboratory tests parameters by treatment group.

Laboratory Test	Parameters
Hematology	Haemoglobin, Haematocrit, Red Blood Cell, Platelets, Mean corpuscular hemoglobin, Mean corpuscular hemoglobin concentration, Mean corpuscular volume, White blood cell count and differential, Erythrocyte sedimentation rate (ESR) ^c
Biochemistry	Alkaline phosphatase (ALP), Aspartate aminotransferase (AST), Alanine aminotransferase (ALT), γ -glutamyl transpeptidase (GGT), Potassium, Sodium, Chloride, Inorganic phosphate, Glucose, Bilirubin (direct and total), C-reactive protein (CRP), Cholesterol, Triglycerides, High density , ipoprotein-cholesterol (HDL), Low density lipoprotein-cholesterol (LDL), Protein (total), Albumin, Creatine phosphokinase (CPK), Creatinine, Ferritin, Calcium Blood urea nitrogen (BUN), hCG ^b
Coagulation	Prothrombin time (PT), International normalized ratio (INR), Activated partial thromboplastin time(aPTT)
Urinalysis	pH, Specific Gravity (Qualitative value): protein, glucose, ketones, urobilinogen, blood Microscopic examination ^a
Serology	Screening only: [REDACTED] [REDACTED] [REDACTED] Baseline (day 1 of Week 1 prior to randomization) and Weeks 16, 26, and 52: [REDACTED]

^a Performed only if required, based on urinalysis results

^b Female subjects of child-bearing potential only; serum pregnancy test will be performed at Visit 1 and a urine pregnancy test at all other site visits and a urine dipstick pregnancy test at home or other home testing arrangements will be performed at Telephone Visits (Visit 6A and 7A).

^c ESR will be analyzed locally at the site level and at Screening only.

All laboratory data will be listed with clinically relevant values flagged (Low = Lower than lower limit of normal range, High = Higher than ULN range or Normal = Normal for or Hematology, Biochemistry, Urinalysis and Coagulation, N=Normal and A=Abnormal for Urinalysis). And then shift table of clinically relevant categories will be presented at post-baseline timepoint. Laboratory Urinalysis Absolute will be summarized by flag (-, +/-, 1+, 2+, 3+, 4+) and analysis visit.

The number and percentage of subjects with potential drug-induced liver function criteria and abnormal liver function criteria at post-baseline timepoint will be summarized.

The figure of mean (or median) and standard error value of ALT, AST, total bilirubin, and ALP by visit will be plotted.

The pregnancy test result (Negative, Positive) will be summarized at each visit.

If laboratory values in central measurement and/or in local site are included, only values in central measurement will be summarized. In addition, all laboratory values including value measured in local site will be also listed.

8.3.3 Vital Signs

Absolute values and change from baseline will be descriptively summarized and shift table of clinically relevant categories (Normal, Not Clinically Significant, Clinically Significant) from baseline to EOT will be presented for the following parameters . All tabulations will be performed by treatment group.

- Systolic Blood Pressure (mmHg)
- Diastolic Blood Pressure (mmHg)
- Pulse Rate
- Respiratory Rate
- Body Temperature (°C)
- Weight (kg)

8.3.4 12-Lead ECGs

Absolute values and changes from baseline will be summarized and shift table of clinically relevant categories (Normal, Not Clinically Significant, Clinically Significant) from baseline to EOT will be presented for the following parameters.

- Heart Rate (bpm)
- RR (msec)

- QRS (msec)
- QT (msec)
- QTcF (msec)
- QTcB (msec)

The percentage of subjects with 12-lead ECG values outside pre-defined limit will be summarized. Number and percentage of subjects meeting the criteria listed 7.1.3.3 will be presented in tables. All tabulations will be performed by treatment group.

8.3.5 Physical Examinations

The number and percentage of the subjects for clinically relevant categories (Normal, Not Clinically Significant, Clinically Significant) will be summarized by treatment group.

- Abdominal
- Respiratory
- Cardiovascular
- General Appearance
- Head
- Eyes
- Ears/nose/throat
- Lymph nodes
- Musculoskeletal
- Neck
- Neurological
- Dermatological
- Other

8.3.6 Nevi appearance

Nevi (Melanocytic Lesions) appearance will be summarized with the number and percentage of the subjects' suspicious nevi (Melanocytic Lesions) found:

- Does the subject have any suspicious nevi found during assessment? (Y,N)
- Has study been temporarily treatment discontinued? (Y,N)
- Has the subject been referred for further evaluation? (Y,N)
- Was the biopsy performed and sent to the central lab? (Y,N)
- Were there any clinically significant findings? (Y,N)

[figure not shown]
All tabulations will be performed by treatment group.

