n. Nevi (Melanocytic Lesions) evaluation will be performed by a local dermatologist or qualified site staff. Baseline nevi (Melanocytic Lesions) evaluation will be performed at any time during the screening period before randomization at Visit 2 (Day 1). The nevi (Melanocytic Lesions) evaluation at Visit 9 is to assess for the reversibility if any suspicious nevi (Melanocytic Lesions) changes that were observed during treatment as per the Investigator's (and/or dermatologist's or other qualified site staff) judgment. Any follow-up will be recorded in the eCRF. Nevi (Melanocytic Lesions) assessment will be described in a separate document.

p. Subjects will be asked whether they believe they received active or placebo treatment.

q. Concomitant medications at screening, baseline, and used during study treatment will be reviewed, recorded and discussed with the Sponsor and medical Monitor (as needed).

r. [REDACTED]

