16.3.5.4 Physical Examination and Nevi (Melanocytic Lesions) Evaluation

Physical examination data will be summarized descriptively (number and percentage of the subjects) in tables by treatment and time point.

Nevi (Melanocytic Lesions) appearance will be summarized descriptively (number and percentage of the subjects) in tables by treatment and analysis visit for subjects' suspicious nevi (Melanocytic Lesions) found.

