6 STATISTICAL CONSIDERATIONS

6.1 Descriptive Statistics

Continuous data will be summarized descriptively using the number in the analysis set (N), the

number of observations (n), mean, standard deviation (SD), median, minimum and maximum. Categorical data will be summarized using frequency counts and percentages. The denominator for the percentages will be the total number of subjects in the treatment group and analysis population being presented, unless otherwise specified (e.g. on some occasions, percentages may be calculated out of the total number of subjects with available data at a particular visit and/or time point).

Unless otherwise specified, all data will be summarized by analysis visits and treatment group.

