For other visits, if there are multiple data in a window, the closest data to nominal day will be used. If the distance to the nominal day is the same, the data of later date will be used.

In the event that in a post baseline visit window there are only values from unscheduled visit, these values will be used to derive the value for this visit.

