9.3 Analysis Visits to Report

Efficacy:

Analysis Visit	Variables											
	ACR	Revised CRISS	mRSS / %pFVC	SH AQ	PTG A/ PHGA	[REDACTED]						
Screening			X								X	
Baseline			X		X		X	X	X			X
Week 2										X		
Week 6						X	X			X		
Week 16	X	X	X	X	X	X	X		X			

Week 26	X	X	X	X	X	X	X	X	X	X	X	X
Week 39	X	X	X	X	X	X	X		X	X	X	X
Week 52	X	X	X	X	X	X	X	X	X	X	X	X
Week 56 (EOS/FU)									X			

Safety:

Analysis Visit	Variables				
	Lab	Vital Signs	ECGs	Nevi	Physical exam
Screening	X	X	X	X	X
Baseline	X	X			X
Week 2	X	X		X	X
Week 6	X	X		X	X
Week 16	X	X			X
Week 26	X	X	X	X	X
Week 39	X	X			X
Week 52	X	X	X	X	X
Week 56 (EOS/FU)	X	X		X	X

Unscheduled visits, retests (same visit number assigned) and follow-up visits will not be displayed in by-visit summary tables, but will be included in the data listings.

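### The nevi table is built by analysis visit, so it gives no count per arm of distinct subjects with a suspicious, referred or biopsied nevus after first dose

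*SAP*

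**What the plan says.** Nevi appearance is a safety endpoint in Protocol 7.2.4 and SAP 2.2.4. SAP 8.3.6 states that "Nevi (Melanocytic Lesions) appearance will be summarized with the number and percentage of the subjects" and lists five yes/no items: suspicious nevi found, treatment temporarily stopped, subject referred, biopsy ("Was the biopsy performed and sent to the central lab? (Y,N)"), and clinically significant findings. It groups them by treatment and does not mention visits.

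The visit dimension comes from elsewhere:

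- Protocol 16.3.5.4: nevi "appearance will be summarized descriptively (number and percentage of the subjects) in tables by treatment and analysis visit".
- SAP 6.1: "Unless otherwise specified, all data will be summarized by analysis visits and treatment group".
- SAP 9.3: the safety grid has a Nevi column, marked at Screening and Weeks 2, 6, 26, 52 and 56. Baseline, Week 16 and Week 39 are blank, and the grid has no ET row.

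Three handling rules also bear on the table. SAP 7.2 says that "if there are multiple data in a window, the closest data to nominal day will be used". It adds that where "there are only values from unscheduled visit, these values will be used to derive the value for this visit". Below the SAP 9.3 grids comes: "Unscheduled visits, retests (same visit number assigned) and follow-up visits will not be displayed in by-visit summary tables, but will be included" in the listings.

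**The concern.** The basic safety question is how many subjects in each arm ever had a suspicious nevus after first dose, and how many were referred or biopsied. It is a pointed question here. Protocol 8.2.2 reports that the only two severe cases in the Phase 1 ascending-dose study, both at 300 mg, were moles that grew, darkened and were excised (benign on histology). This trial starts at 300 mg.

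A table of Yes answers by visit does not answer that question, because the same subject can appear in several rows. The protocol makes repeat counting plausible: the Table 1 note says that the nevi "evaluation at Visit 9 is to assess for the reversibility if any suspicious nevi" changes seen on treatment persist, so a lesion counted earlier may be counted again at Week 56.

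Elsewhere the SAP does summarise over the whole post-baseline period. The liver criteria in 7.1.3.2 apply at any post-baseline timepoint, and 8.3.1 has a subject-level hyperpigmentation TEAE category. Nevi have neither.

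**Working it through.** The plan states no figure on this point, so there is none to reproduce. The check is a reading of the rules plus simple bounds.

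**1. Is the table by visit?** SAP 8.3.6 is silent on visits. SAP 6.1 makes analysis visit the default unless a section says otherwise, and 8.3.6 does not. SAP 9.3 gives nevi its own visit column. Protocol 16.3.5.4 agrees. The by-visit reading therefore follows from the SAP alone. If 8.3.6 were instead read as one overall table, it would still lack a rule for combining repeated answers and would not exclude the Screening exam.

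**2. What do visit counts say about subjects?** Inputs: 36 planned per arm (Protocol 9.1), and V nevi rows after first dose (SAP 9.3), where V = 4 (Weeks 2, 6, 26, 52), or 5 if Week 56 is displayed. If k of 36 subjects are Yes at each visit, the number ever Yes lies between k (the same subjects each time) and min(36, V × k) (different subjects each time). The documents give no nevus rate, so k is assumed.

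| k per visit | V = 4 | V = 5 |
|---|---|---|
| 1 (1/36 = 2.8%) | 1 to 4 (2.8% to 4/36 = 11.1%) | 1 to 5 (2.8% to 5/36 = 13.9%) |
| 2 (2/36 = 5.6%) | 2 to 8 (5.6% to 8/36 = 22.2%) | 2 to 10 (5.6% to 10/36 = 27.8%) |

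Two arms could show the same rows throughout while 2 subjects in one and 10 in the other were ever positive.

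**3. Which exams can be absent from the table?** The windows are from the SAP 7.2 table that applies to nevi.

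| Exam | Outcome under SAP 7.2 and 9.3 |
|---|---|
| Unscheduled, alone in the Week 2, 6, 26 or 52 window | Used under 7.2, though the 9.3 sentence on unscheduled visits leaves some doubt |
| Unscheduled, further from the nominal day than another exam in its window | Not used, even if it is the only positive one |
| Unscheduled, Days 78–147 (Week 16) or 229–319 (Week 39) | No nevi row |
| ET, mapped to the ET analysis visit | No ET row |
| ET, mapped by study day | Row exists for Days 2–77, 148–228 and 320–379; none for Days 78–147 or 229–319 |
| Week 56 | Marked in the grid, but the sentence below says follow-up visits are not displayed |

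The unscheduled routes arise only if a nevi exam is done at such a visit, which Protocol 10.1.6 leaves to the investigator. The SAP does not say which mapping applies to ET exams.

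**4. What do other outputs cover?** Under Protocol 12.4, suspicious nevi of clinical concern lead to interruption and to referral as needed, and nevi of clinical concern must be recorded as AEs. SAP 8.3.1 counts a subject once per SOC and PT. SAP 8.1.10 tabulates interruptions with reasons. SAP 8 lists all data. None of these tables carries referral or biopsy status, and none includes a suspicious nevus that was not judged of clinical concern.

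**The case against.** The strongest reply is that SAP 8.3.6 never says by visit, and that SAP section 1 lets SAP analysis details override the protocol, which weakens Protocol 16.3.5.4 as support. Table shells are not in the documents, and the 9.3 column does not forbid an overall row. This does not remove the point: the by-visit default is in the SAP itself, and no text defines an overall row.

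The second reply is that the content is largely counted already. For nevi of clinical concern this stands in good part, since one trigger drives interruption, referral and AE recording, and the TEAE and interruption tables count subjects. With about 36 per arm, a reader could also count from the listing. Visit-wise display suits the Visit 9 purpose of checking reversibility, so the by-visit table should stay.

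Three stronger readings should be resisted:

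- A reader might infer that every ET nevi exam drops out. Mapped by day, an ET exam may land in a displayed window. The missing ET row also affects every safety variable in the 9.3 grid and is not peculiar to nevi.
- A reader might infer that nevus AEs will scatter over several PTs and so defeat the TEAE tables. That depends on coding that the documents do not show.
- A reader might take the ranges above as estimates of missed findings. They are bounds on assumed counts.

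**Conclusion.** The concern holds as a minor reporting gap. As planned, the nevi table will not show how many distinct subjects per arm had a suspicious, referred or biopsied nevus after first dose, and a positive unscheduled or ET exam may be absent from it. What no other table summarises is mainly referral status, biopsy status and suspicious nevi not judged of clinical concern.

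The effect is confined to one descriptive table. It would be wrong to infer that nevi findings are lost or that subjects are less protected: the data are collected and listed, Protocol 12.4 governs action, and no test or efficacy estimate changes. The number of exams absent from the table is unknown and may be zero. The conclusion rests on the by-visit reading from SAP 6.1 and 9.3. The percentages assume 36 per arm and the chosen visit counts.

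**What to change.** In SAP 8.3.6, add for each of the five items one row counting subjects with a Yes at any time after first dose, by treatment group on the Safety population. Take the worst answer over all scheduled, unscheduled, ET and follow-up assessments. Keep the by-visit table as secondary. In SAP 9.3, state whether the Week 56 nevi row is displayed. The cost is a few lines of SAP text and one extra descriptive table from data already collected.

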8.4 Pharmacokinetics Evaluation

Pharmacokinetics evaluation will be made on the PK population. Plasma MT-7117 concentrations will be listed for each subject. Plasma concentrations of MT-7117 will be analyzed at randomization visit (Day 1 pre-dose), Week 2 (any time), Week 6 (any time), Week 16 (any time), Week 26(any time), Week 39(any time), and Week 52 (any time). PK sample collection times, most recent dosing times before PK sample collection, as well as derived actual sampling time relative to the most recent dose will be provided in a listing. The actual sampling time relative to the most recent dose will be calculated in hours and rounded to 2 DP and the mean values of actual sampling time will be calculated for each visit. Plots of individual concentration vs actual sampling time will be presented overlaid with treatment in different symbols for each treatment and overlaid with visit. For the calculation of the summary statistics (mean, SD, minimum, median, and maximum) of plasma concentrations at each sampling point, concentration values reported as below the limit of quantification (BLQ) will be set to 0.

Population PK analysis will be performed using the plasma concentration of MT-7117 obtained in this study in combination with data obtained from other clinical studies. Population PK analysis results will be reported separately as necessary.

8.5 Pharmacogenetics Evaluation

8.6 Exploratory endpoint

A series of horizontal black bars of varying lengths, some with small white squares at their ends, arranged in a descending staircase pattern. The bars are positioned in a grid-like structure, with each row containing one less bar than the row above it. The lengths of the bars decrease from left to right across each row. Some bars have small white squares at their ends, which appear to be aligned with the centers of the bars in the row below. The overall effect is a visual representation of a descending staircase or a series of steps.

9 DATA PRESENTATION CONVENTIONS

9.1 Number of Digits to Report

(1) Non-PK related

Statistic	Specification	Apply to
Minimum, Maximum	Same number of DPs as the data provided in the datasets	All original (i.e. non-derived)
		All derived data
Mean, Median, SD, SE, Confidence intervals	One more DP than above	All
Percentages ^{*1}	1 DP	All
Ratios	3 DPs	All
p-values ^{*2}	3 DPs	All

*1 Percentages: use 1 place beyond the decimal point, except for the following cases:

If the percentage is equal to 0, then leave blank, do not use (0)

If the percentage is equal to 100, then use “(100)” without a decimal

*² p-values: use 3 places beyond the decimal point, except for the following cases:

If the p-value is less than 0.001, then use p<0.001

(2) Plasma concentration

Statistic	Specification
-----------	---------------

Individual value, Mean, SD, Minimum, Maximum, Median	The same significant digits as they are reported
---	--

9.2 Treatment Groups to Report

Unless otherwise specified, the following treatment groups will be reported.

Treatment Group	For TTEs
MT-7117 [REDACTED] with dose reduction to [REDACTED]	MT-7117
Placebo	Placebo

For only CRISS score and mRSS, the following treatment groups will be reported as the secondary analysis.

Treatment Group	For TTEs
MT-7117 [REDACTED]	MT-7117 [REDACTED]
MT-7117 [REDACTED]	MT-7117 [REDACTED]
MT-7117 [REDACTED]	MT-7117 [REDACTED]
Placebo	Placebo

9.3 Analysis Visits to Report

Efficacy:

Analysis Visit	Variables											
	ACR	Revised CRISS	mRSS / %pFVC	SH AQ	PTG A/ PHGA	[REDACTED]						
Screening			X								X	
Baseline			X		X		X	X	X			X
Week 2										X		
Week 6						X	X			X		
Week 16	X	X	X	X	X	X	X		X			

Week 26	X	X	X	X	X	X	X	X	X	X	X	X
Week 39	X	X	X	X	X	X	X		X	X	X	X
Week 52	X	X	X	X	X	X	X	X	X	X	X	X
Week 56 (EOS/FU)									X			

Safety:

Analysis Visit	Variables				
	Lab	Vital Signs	ECGs	Nevi	Physical exam
Screening	X	X	X	X	X
Baseline	X	X			X
Week 2	X	X		X	X
Week 6	X	X		X	X
Week 16	X	X			X
Week 26	X	X	X	X	X
Week 39	X	X			X
Week 52	X	X	X	X	X
Week 56 (EOS/FU)	X	X		X	X

Unscheduled visits, retests (same visit number assigned) and follow-up visits will not be displayed in by-visit summary tables, but will be included in the data listings.

10 CHANGE FROM THE PROTOCOL

- “The total number (%) of subjects in each analysis populations” in Subject Disposition was changed to “Number (%) of subjects in the ITT population”.
- Year of birth was deleted from “Demographic and Other Baseline Characteristics”.
- The “baseline mRSS by visit interaction” was deleted from generalized linear mixed effect model of “ACR CRISS score responder (CRISS ≥ 0.6)”.

- The “Revised CRISS” and “new Revised CRISS” will be analyzed using generalized linear mixed effect model.
- “ACR CRISS Score improvement at Weeks 16, 26, 39 and 52: Proportion of subjects with $\geq 25\%$ improvement in mRSS, HAQ DI, Patient Global Assessment, Physician Global Assessment, or $\geq 5\%$ improvement in FVC for at least 3 of the 5 ACR CRISS measures.” was deleted from 8.2.2 Secondary Efficacy Endpoints, because “the revised CRISS at each timepoint with \geq the predefined 25% improvement in mRSS, HAQ-DI, PtGA and PhGA, or $\geq 5\%$ improvement in %pFVC for at least 2 of the 5 core set measures and the revised CRISS at each timepoint with \geq the predefined 25% worsening in mRSS, HAQ-DI, PtGA and PhGA, or $\geq 5\%$ worsening in %pFVC for no more than 1 of the 5 core set measures” was analyzed in “new Revised CRISS” of 8.2.3 Exploratory Efficacy Endpoints.
- Following abnormal liver function criteria was changed.
ALT was changed from “ $\geq 2^*\text{ULN}$, $\geq 3^*\text{ULN}$ ” to “ $>2^*\text{ULN}$, $>3^*\text{ULN}$, $>5^*\text{ULN}$, $>8^*\text{ULN}$ ”.
AST was changed from “ $\geq 2^*\text{ULN}$, $\geq 3^*\text{ULN}$ ” to “ $>2^*\text{ULN}$, $>3^*\text{ULN}$, $>5^*\text{ULN}$, $>8^*\text{ULN}$ ”.
GGT was changed from “ $\geq 2^*\text{ULN}$, $\geq 3^*\text{ULN}$ ” to “ $>2.5^*\text{ULN}$, $>5^*\text{ULN}$, $>8^*\text{ULN}$ ”.
ALP was changed from “ $\geq 2^*\text{ULN}$, $\geq 3^*\text{ULN}$ ” to “ $>1.5^*\text{ULN}$, $>2.5^*\text{ULN}$, $>5^*\text{ULN}$ ”.
Direct and total bilirubin was changed from “ $\geq 2^*\text{ULN}$, $\geq 3^*\text{ULN}$ ” to “ 1.5^*ULN , $>2^*\text{ULN}$, $>3^*\text{ULN}$ ”.
- Standard errors of ALT, AST, total bilirubin, and ALP by visit were changed to standard deviations.

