2 STUDY OBJECTIVE AND ENDPOINTS

2.1 Study Objectives

Primary:

- To evaluate the efficacy of MT-7117 treatment in subjects with diffuse cutaneous systemic sclerosis (dcSSc) using the American College of Rheumatology Composite Response Index in Diffuse Systemic Sclerosis (ACR CRISS) at Week 52.

Secondary:

- To evaluate the efficacy of MT-7117 treatment for up to 52 weeks using patient-reported outcomes (PROs) as measured by the Health Assessment Questionnaire Disability Index (HAQ-DI) and Patient Global Assessment.
- To evaluate the efficacy of MT-7117 treatment for up to 52 weeks on pulmonary function as measured by percent predicted forced vital capacity (%pFVC).
- To evaluate the efficacy of MT-7117 treatment for up to 52 weeks using the Physician Global Assessment.
- To evaluate the efficacy of MT-7117 treatment for up to 52 weeks using the modified Rodnan Skin Score (mRSS).
- To evaluate ACR CRISS at Weeks 16, 26, and 39.

- To evaluate ACR CRISS Score improvement proportion up to 52 weeks.

Exploratory:

Safety:

- To evaluate the safety and tolerability of MT-7117 treatment for up to 56 weeks in subjects with dcSSc.

Pharmacokinetics:

- To determine the pharmacokinetic (PK) profile of MT-7117 in subjects with dcSSc.

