2.2.2 Secondary Efficacy Endpoints

- Change in HAQ-DI from baseline at Weeks 16, 26, 39, and 52.
- Change in Patient Global Assessment from baseline at Weeks 16, 26, 39, and 52.
- Change in percent predicted forced vital capacity (%pFVC) from baseline at Weeks 16, 26, 39, and 52.
- Change in Physician Global Assessment from baseline at Weeks 16, 26, 39, and 52.
- Change in mRSS from baseline at Weeks 16, 26, 39, and 52.
- ACR CRISS Score at Weeks 16, 26, and 39.
- ACR CRISS Score improvement at Weeks 16, 26, 39 and 52: Proportion of subjects with $\geq 25\%$ improvement in mRSS, HAQ-DI, Patient Global Assessment, Physician Global Assessment, or $\geq 5\%$ improvement in FVC for at least 3 of the 5 ACR CRISS measures.
- ACR CRISS score responder (CRISS ≥ 0.6) at Weeks 16, 26, 39, and 52..

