7.1.2.2 Secondary Efficacy Endpoints

- ACR CRISS Responder

An ACR CRISS score of 0.60 or greater indicates that a subject improved on treatment and a score of less than 0.6 suggests that a subject has not improved.

- HAQ-DI

The HAQ-DI is a self-administered instrument that measures physical disability in 8 different domains of function: dressing/grooming, arising, eating, walking, hygiene,

reach, grip, and common activities. Subjects are asked about 2 or 3 activities associated with each category and choose whether they are able to perform the activity ‘without any difficulty’, ‘with some difficulty’, ‘with much difficulty’, or ‘unable to do’. An additional section asks subjects to indicate if they used any aids or devices or needed assistance to perform daily activities.

A negative change from baseline indicates improvement. The Minimal Clinically Important Difference (MCID) for improvement ranges from 0.14-0.22 (Khanna et al. 2006; Pope 2011)

HAQ-DI is calculated based on the following points.

- There are four possible response for each component:
 - Without ANY difficulty = 0
 - With SOME difficulty = 1
 - With MUCH difficulty = 2
 - UNABLE to do = 3
- A category score is determined from the highest score of the components in that category (except when aids and devices are taken into account; see below). For example, if there are three components in a category and the responses were 1, 2 and 0 to the components in the category, then the score for the category would be 2.
- If a category consists of only two questions
- and has one missing response, then the non-missing response will be used as the value for the category. If a category consists of three questions and has one missing response, then the category score will be the higher of the two responses. If a category consists of three questions and has two missing responses, then the category will be considered missing.
- To calculate the HAQ-DI, the patient must have a category score for at least six of the eight categories. The HAQ-DI is the sum of the category scores, divided by the number of categories that have a score.

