8.2 Efficacy Assessments

All efficacy endpoints will be summarized using descriptive statistics or using the number with percentage and presented in data listing.

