8.2.2 Secondary Efficacy Endpoints

Continuous endpoint

Change from baseline at 16, 26, 39 and 52 in the followings;

[figure not shown]
- HAQ-DI
- Patient Global Assessment
- %pFVC
- Physician Global Assessment
- mRSS

The above endpoint will be analyzed using mixed-effect model for repeated measures (MMRM). The model will include fixed categorical terms for treatment, randomization strata (autoantibody status of anti-RNA Polymerase III at screening (positive or negative)), visit, and treatment by visit interaction together with continuous covariate terms for baseline value of the endpoint and baseline value by visit interaction. An unstructured correlation structure will be used to model the within-subject variance covariance errors. Should convergence of the model fail (due to the small numbers of subjects in this study), other variance covariance matrices such as autoregressive [AR(1)] correlation matrix will be used if appropriate. The Kenward-Roger approximation will be used to estimate the denominator degrees of freedom. From the model

described above, adjusted (least squares [LS]) means and standard errors will be produced by treatment and visit. Difference in adjusted means at each visit (MT-7117 vs. placebo) with standard errors, 95% CIs and associated P values will also be produced. All available data from all subjects will be used in the analysis without any imputation.

ACR CRISS score responder (CRISS \geq 0.6)

Proportion of subjects with ACR CRISS score responder (CRISS \geq 0.6) at Weeks 16, 26, 39, and 52 will be analyzed using logistic regression model employing SAS GLIMMIX procedure. The model will include fixed categorical terms for the treatment group (TRTPN), the randomization factor (screening autoantibodyanti-RNA Polymerase III, positive or negative - STRTNC), visit, and treatment group (TRTPN) by visit interaction together with continuous covariate terms for baseline mRSS (BLMRSS). The treatment odds ratio at each visit will be estimated using a contrast (using ilink PDIFF options in LSMEANS). An unstructured correlation structure (UN) will be used to model the within-subject variance covariance errors. Should convergence of the model fail (due to the small numbers of subjects in this study), other variance covariance matrices such as autoregressive [AR(1)] or compound symmetry (CS) correlation matrix will be used if appropriate. The following SAS code will be used.

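### The SAP still lists the 3-of-5 ACR CRISS improvement proportion as secondary, but SAP 8.2.2 gives it no treatment comparison, and SAP 10 drops that comparison by pointing to a different, non-nested exploratory rule

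*SAP*

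**What the plan says.** SAP 2.1 keeps the secondary objective "To evaluate ACR CRISS Score improvement proportion up to 52 weeks". SAP 2.2.2 keeps the matching endpoint at Weeks 16, 26, 39 and 52: at least 25% improvement in mRSS, HAQ-DI or either global assessment, or at least 5% "improvement in FVC for at least 3 of the 5 ACR CRISS measures". Protocol 7.1.2 and 7.2.2 say the same.

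Protocol 16.3.4.2 analyses this proportion at Week 52 by logistic regression on treatment, the randomisation factor and baseline mRSS. It reports a treatment odds ratio and counts missing core-set data as non-improvement.

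Readable SAP 8.2.2 covers two things: the five component changes, by a repeated-measures model, and the responder defined by a CRISS score of at least 0.6, which "will be analyzed using logistic regression model employing SAS GLIMMIX procedure". That responder is a cut-off on the composite score (SAP 7.1.2.2: "An ACR CRISS score of 0.60 or greater indicates that a subject improved on treatment"), not a count of improved measures. SAP 10 states that the 3-of-5 endpoint "was deleted from 8.2.2 Secondary Efficacy Endpoints" and gives as the reason that the new Revised CRISS is analysed among the exploratory endpoints in SAP 8.2.3. It prints that rule: at least 2 of 5 improved and no more than 1 of 5 worsened.

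Two general sentences still reach the 3-of-5 endpoint. SAP 8.2: "All efficacy endpoints will be summarized using descriptive statistics or using the number with percentage". SAP 6.1: "Unless otherwise specified, all data will be summarized by analysis visits and treatment group". SAP 1 gives the SAP's analysis details precedence over the protocol's.

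**The concern.** Sections of the same SAP that are all in force disagree. One part declares a secondary endpoint; another removes its only planned between-group comparison. The reason offered is that a different endpoint, one tier lower, is analysed instead. That reason would work only if the second rule carried the information of the first. If it does not, the study report will list a secondary objective without the treatment estimate that the protocol promised, and a reader of SAP 10 may take the exploratory result as the answer to it.

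**Working it through.** **The plan's own figure.** The documents give no rate or power for this endpoint. The only design figure is 80% power for the primary test (SAP 3.3). It reproduces: P(X<Y) = Φ(0.35/(0.5√2)) = 0.690, and Noether's formula then gives 79.6% at N = 72. It does not bear on this point.

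**Step 1. Are the rules nested?** Class each of the 5 measures as improved, unchanged or worsened, giving 3^5 = 243 patterns. Let i be the number improved and w the number worsened. Rule A (SAP 2.2.2) is i ≥ 3. Rule B (SAP 10) is i ≥ 2 and w ≤ 1. Both are taken to use the same five measures and thresholds.

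- A: 10×4 + 5×2 + 1 = 51.
- B: (32 − 1 − 5) with w = 0, plus 5×(16 − 1 − 4) with w = 1, so 26 + 55 = 81.
- Both: 16 with w = 0 plus 25 with w = 1, so 41.
- A only: 51 − 41 = 10, all with 3 improved and 2 worsened.
- B only: 81 − 41 = 40, of which 10 have 2 improved and 0 worsened, and 30 have 2 improved and 1 worsened.

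Neither rule contains the other. These are counts of logical patterns, not frequencies of patients, and they need no assumption about rates.

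**Step 2. How far could the results differ?** Every input here is an assumption: a common improvement rate p and worsening rate q per measure, and a common correlation r. The Step 1 organ-worsening component of the composite is ignored. With u = 1 − p − q and r = 0:

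- P(A) = Σ C(5,k) p^k (1−p)^(5−k) for k = 3 to 5.
- P(B) = [(1−q)^5 − u^5 − 5pu^4] + 5q[(1−q)^4 − u^4 − 4pu^3].

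Worked example, q = 0.25 in both arms, p = 0.30 on placebo and 0.50 on active:

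- A: 0.500 − 0.163 = 0.337.
- B: 0.578 − 0.365 = 0.213.
- Gap: 12.4 points.

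For r > 0 the same quantities come from an equicorrelated latent normal model. Contrasts are active minus placebo, in percentage points, A v B:

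| Assumed change | r = 0 | r = 0.5 | r = 0.7 |
|---|---|---|---|
| p 0.30 to 0.45, q 0.15 in both arms | 24.4 v 23.3 | 18.1 v 18.2 | not run |
| p 0.30 to 0.50, q 0.25 in both arms | 33.7 v 21.3 | 24.3 v 19.1 | 22.3 v 20.3 |
| p 0.30 in both arms, q 0.30 to 0.15 | 0 v 10.3 | 0 v 2.4 | 0 v 0.6 |

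In the second row the gap falls from 12.4 to 5.2 to 2.0 points as r rises. The third row shows the difference in kind: a drug that only prevents worsening moves B and leaves A at zero.

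At p = 0.30 and q = 0.15 in a single group, the share meeting B but not A is 27.2%, 15.4% and 11.0% at r = 0, 0.5 and 0.7 (about 20, 11 and 8 of 72). The share meeting A but not B is 0.6% or less. It becomes material only when worsening is common: at p = 0.50 and q = 0.40 it is 20.0% at r = 0 and 7.9% at r = 0.5.

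**The case against.** **The change is declared.** SAP 10 restates the endpoint, says where it was removed, gives a reason and prints the replacement. Protocol 16 allows justified changes. This stands against any reading that an analysis was quietly dropped. It does not reconcile SAP 2.1 and 2.2.2 with 8.2.2, and it does not make the reason valid.

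**The analysis may sit in redacted text.** SAP 7.1.2.3 and 8.2.3 are blacked out. A separate Revised CRISS is reported at Weeks 16 to 52 (SAP 9.3) and modelled (SAP 10). A reader might infer that the 3-of-5 proportion gets no treatment comparison anywhere; the documents do not support that. What they do show is that it has none as a secondary endpoint. The tier matters less than usual, because the readable plan tests everything at two-sided 0.05 with no hierarchy (SAP 6.2). That is a reason for low priority, not for leaving the conflict.

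**There may still be a missing-data rule.** A reader might infer that none applies. SAP 1 displaces the protocol only where the SAP describes something, and SAP 10 states no substitute, so the protocol's rule can be read as still governing the counts. The point is arguable and is not pressed. Likewise FVC in SAP 2.2.2 almost certainly means %pFVC, since Protocol 11.4 names %pFVC among the five measures.

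**Restoring the model covers Week 52 only.** True, but that is what the protocol planned; the other visits were left without a model for this endpoint there too.

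**The illustration proves no harm.** Correct. All rates are assumed, the widest gap needs independent measures, and in one scenario the rules agree to about a point.

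**Conclusion.** The point holds as a consistency defect of low priority that should still be corrected. A declared secondary endpoint has descriptive counts but, in readable text, no secondary treatment estimate, and the stated reason for removing that estimate rests on a rule that measures something else. The non-nesting is a matter of logic and needs no assumption beyond common measures and thresholds. The size does: 12.4 points is the widest of three assumed scenarios, not a bound, and with correlated measures the gap there is 5.2 or 2.0 points.

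A reader might go further and infer that the primary result, the CRISS ≥ 0.6 responder or the component analyses are affected. Nothing in the documents supports that, and no effect on the trial's conclusion is claimed.

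**What to change.** Preferred course:

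1. Restore to SAP 8.2.2 the Week 52 logistic regression of Protocol 16.3.4.2: treatment, randomisation stratum and baseline mRSS, with missing counted as non-improvement. Leave the counts and percentages at Weeks 16, 26, 39 and 52 as they are.
2. Add a short derivation to SAP 7.1.2.2 stating that the FVC measure is %pFVC. When carrying the protocol text over, check its reference to Step 1 of Section 11.4, which in readable text describes organ worsening. Appendix 4's title is partly redacted, so this is a query, not an error.
3. Keep the new Revised CRISS exploratory and remove it from SAP 10 as the reason for the deletion.

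Cost: one model, one table and a few lines of text, on data already collected.

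If the sponsor does not want the analysis, it should reclassify the objective and endpoint as descriptive, or remove them, in SAP 2.1 and 2.2.2. SAP 10 should record this as a departure from Protocol 7.1.2 and 7.2.2, with a reason that does not rely on the two rules being equivalent, and the study report should carry it as Protocol 16 requires. Cost: edits to three SAP sections and one entry in the report.
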